4.3.7. Additional Part C Assessments

4.3.7.1. Endpoints/Variables

F, FA, FG and FH, CL, tmax and t_{1/2} following single IV / oral doses of GSK3915393 alone/with water or with ITZ/GFJ

4.3.7.2. Summary Measure

F, FA, FG, FH and CL would be summarized. tmax and t_{1/2} would be summarized by regimen. .

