### Part C

Part C consists of 5 single dose periods of GSK3915393. In period 1, all participants will receive an IV microdose of GSK3915393. In period 2 all participants will receive oral doses of itraconazole for 6 days and an IV microdose of GSK3915393 on the 4th day of itraconazole dosing. In periods 3 and 4, participants will receive oral GSK3915393 with water or with grapefruit juice in a randomized crossover design. In period 5, all participants will receive oral doses of itraconazole for 6 days and a single oral dose of GSK3915393 on the 4th day of itraconazole dosing. A sufficient number of healthy participants will be screened to enroll 12 participants. Participants will be randomized to one of the 2 sequences shown in [Table 2](#). Participants will participate in 5 dosing periods and will receive an IV microdose of GSK3915393 in periods 1 and 2 and three active oral doses of GSK3915393 in periods 3, 4 and 5; either dosed alone, with grapefruit juice or with itraconazole. Participants will be dosed in the fasted state.

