Since expression of intestinal CYP3A4 is altered in patients with CeD, determining the impact of intestinal CYP3A4 on the predicted exposure of GSK3915393 in the lamina propria (the site of TG2 activity in CeD) is important to understand the predicted pharmacological activity of GSK3915393 in patients. Grapefruit juice administered as a single dose has been shown to inhibit CYP3A4 gut metabolism but not CYP3A4 hepatic metabolism, so in Periods 3 and 4 of Part C, GSK3915393 will be administered with and without coadministration of grapefruit juice (GFJ) to determine the fraction of GSK3915393 which escapes gut metabolism by CYP3A4 in healthy volunteers. Coadministration of GSK3915393 with GFJ will occur in either period 3 or 4, per the randomization schedule, to minimize impact of period effects to the GFJ interaction assessments.

Itraconazole 200mg will be dosed for 6 days with GSK3915393 dosed on Day 4. The 3-day lead-in of ITZ dosing allows for accumulation of ITZ to maximise the degree of CYP3A4 inhibition. Continuing to dose ITZ on Days 5 and 6 will maintain maximal CYP3A4 inhibition to fully characterise the impact of ITZ on the elimination of GSK3915393. Since the half-life of GSK3915393 may be significantly extended upon coadministration with itraconazole, there is increased potential for carryover effects after these regimens compared to the other regimens. For this reason, the itraconazole regimens will be given in fixed periods (2 and 5) rather than in randomized sequence. An extended washout period of at least 7 days is incorporated between periods 2 and 3.

Holter monitor data will be collected and stored for future evaluation of the correlation between plasma levels of GSK3915393 and changes in the QTc interval, if appropriate. Emerging literature suggests that frequent QT evaluation early in development may mitigate the need for a formal thorough QT/QTc (TQT) study [Darpo, 2014]. Therefore, Holter monitor data will be collected during Parts A and B of this study. This data will be held by ERT and may be analysed in the future, if necessary, for a potential TQT waiver in further development of the compound. This will not be reported in the primary clinical study report (CSR).

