#### 9.4.1. Primary Endpoint(s)

In parts A and B, the primary endpoints are the safety assessments as detailed in Section 3.

Safety data will be summarised in tabular and/or graphical form by dose regimen over time for the safety population. Data for each study part will be summarised separately.

In part C, the primary endpoints are GSK3915393 pharmacokinetic parameters AUC, Cmax, Tmax and t1/2 and these are outlined alongside the pharmacokinetic endpoints for parts A and B within Section 9.4.2.

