### Part C (CYP3A4 victim assessment)

- Cmax
- Tmax
- AUC(0-t)
- AUC(0-∞) and t1/2, if data allow
- $F_G = AUC_{H2O} \div AUC_{GFJ}$  (oral administration of GSK3915393)
- F,  $F_A$ ,  $F_H$ :
  - F and  $F_H$  are defined as above under Part A
  - $F_A = (F \div F_H) \div F_G$

Pharmacokinetic data will be presented in graphical and/or tabular form and will be summarized descriptively.

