Primary 3 (Part C)	
 • Cmax, • tmax, • AUC(0-t), • AUC(0-∞) and • t_{1/2} 	
 • All Intercurrent Events – a treatment policy approach will be applied such that all available data will be included in analyses. For subjects with partial concentration-time data on a given study period, derived parameters such as AUC will be available on that study period provided there are sufficient concentration data to enable their estimation 	Descriptive statistics Point estimates and 90% CI for ratios of AUC or Cmax for GSK3915393 IV with ITZ vs GSK3915393 IV.
Primary Objective (4): To characterize the PK profile of oral GSK3915393 administered alone and when co-administered with grapefruit juice or with itraconazole in healthy adult participants			
Primary 4 (Part C)	As defined for Primary Objective 3	As Defined for Primary Objective 3	As Defined Primary for Objective 3 Point estimates and 90% CI for ratios of AUC or Cmax for GSK3915393 PO with GFJ vs GSK3915393 PO with water and GSK3915393 PO with ITZ vs GSK3915393 PO with water

Estimand Category	Estimand		
	Variable/ Endpoint	Intercurrent Event Strategy	Population Level Summary Measure
Secondary Objective (1): To characterize the PK profile of single oral doses of GSK3915393 in healthy adult participants			
Secondary 1 (Part A)	
 • AUC (0-∞) • AUC (0-t) • Cmax • t_{max} • t_{1/2} • Absolute bioavailability (F) • F_H • F_A*F_G 	As Defined for Primary Objective 3	Descriptive Statistics
Secondary Objective (2): To characterize the PK profile of single intravenous doses of GSK3915393 in healthy adult participants			
Secondary 2 (Part A)	
 • AUC (0-∞) • AUC (0-t) • Cmax • T_{max} • t_{1/2} • Clearance (CL) (IV only) • Volume of distribution (V_d) (IV only) 	As Defined for Primary Objective 3	Descriptive Statistics
Secondary Objective (3): To evaluate the safety and tolerability of single microdose doses of GSK3915393 in healthy adult participants.			
Secondary 3 (Part A)	As defined for Primary Objective 1	As defined for Primary Objective 1	As defined for Primary Objective 1
Secondary Objective (4): To characterize the PK profile of single doses and repeat oral doses of GSK3915393 in healthy adult participants.			

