4.3.4.2. Main Analytical Approach

For each dose level separately, Log_e-transformed AUC(0- τ) and Cmax after 1st dose (on days 3, 5 and 7) will be statistically analysed using a Mixed effects model with:

- Prandial state ~ (high fat (day 5 data), standard meal (day 7 data) or fasted (day 3 data))
- participant as random effect

The Kenward and Roger method for approximating the denominator degrees of freedom and correcting for bias in the estimated variance-covariance of the fixed effects will be used. An unstructured type of the covariance matrices R (accounting for the within participant variability) and G (accounting for the between participant variability) will be used.

The estimated geometric mean ratios and 90% CI for (high fat meal: fasted) and (standard meal: fasted) will be derived for each dose (i.e., Low dose, Medium dose and High dose).

Distributional assumptions underlying the model used for analysis will be examined by obtaining a normal probability plot of the residuals and a plot of the residuals versus the fitted values (i.e. checking the normality assumption and constant variance assumption of the model respectively) to gain confidence that the model assumptions are reasonable. If there are any departures from the distributional assumptions, alternative transformations, such as data squared or square root of data, will be explored. Non-parametric analyses will be conducted if the normality assumption does not hold for any of the alternative transformations. If this model fails to converge, alternative covariance structures may be considered in the following order (1) Compound Symmetry (CS) and (2) Variance Components (VC).

tmax after 1st dose on day 3 and day 5 will be analysed non parametrically applying a Wilcoxon signed rank test and a point estimate and distribution free 90% CI for the median difference in tmax for (high fat meal vs fasted) will be derived by specifying the CIQUANTDF option in SAS Proc Univariate. The analysis will be repeated for tmax after 1st dose on days 3 and day 7 to derive point estimate and distribution free 90% CI for the median difference of (standard meal vs fasted).

4.3.5. CYP3A4 victim assessment – Impact of Grapefruit Juice (Part C)**4.3.5.1. Endpoints/Variables**

AUC (0-∞) [or AUC (0-t) or AUC (0-τ)], Cmax following single oral doses of GSK3915393 with water or with GFJ.

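### Part C lists tmax and t1/2 as primary endpoints in a within-participant design, but the SAP plans no within-participant contrast with an interval for them

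*SAP*

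**What the plan says.** Protocol 9.4.1 states: "In part C, the primary endpoints are GSK3915393 pharmacokinetic parameters AUC, Cmax, Tmax and t" (the last item is t1/2). Section 3 of the protocol and SAP 1.1.1 list the same parameters.

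Part C is a within-participant design. Protocol 4.1.2 says: "Participants will participate in 5 dosing periods and will receive an IV microdose of GSK3915393 in periods 1 and 2", followed by three oral periods: with water, with GFJ and with itraconazole (ITZ). The order of water and juice is randomised; the ITZ periods are fixed. On numbers: "A sufficient number of healthy participants will be screened to enroll 12 participants".

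For Primary 3, SAP Table 2 gives descriptive statistics and then: "Point estimates and 90% CI for ratios of AUC or Cmax for GSK3915393 IV with ITZ vs GSK3915393 IV". Primary 4 does the same for the two oral comparisons. The mixed models in SAP 4.3.5.2 and 4.3.6.2 cover AUC and Cmax only. For the remaining primary endpoints SAP 4.3.7.2 says: "tmax and t_{1/2} would be summarized by regimen".

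Two other places bear on this. Protocol 9.4.2 says of Part C: "Pharmacokinetic data will be presented in graphical and/or tabular form and will be summarized descriptively". In the Part B food-effect analysis, where tmax is secondary, SAP 4.3.4.2 says: "tmax after 1st dose on day 3 and day 5 will be analysed non parametrically applying a Wilcoxon signed rank test", with a median difference and a distribution-free 90% CI.

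**The concern.** Primary objectives 3 and 4 set the PK profile of the drug alone beside its profile with an inhibitor, in the same people. For AUC and Cmax the plan uses that pairing. For t1/2 and tmax it reports each regimen separately, so the spread shown includes differences between participants, which the design was able to remove. SAP Section 2 says point estimates and CIs will be constructed where appropriate, and no reason is given for stopping short here.

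Two uses are affected.

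- **Itraconazole.** Protocol 4.2 expects that half-life may lengthen and explains the extra inhibitor doses: "Continuing to dose ITZ on Days 5 and 6 will maintain maximal CYP3A4 inhibition to fully characterise the impact of ITZ on the elimination of" the study drug. Any lengthening of t1/2 would be reported without a ratio or an interval.
- **Grapefruit juice.** The footnote to SAP Table 3 says F_G is valid only if juice inhibits gut but not hepatic CYP3A4. F_G then feeds the lamina propria exposure prediction in protocol 9.4.3.1. A juice-to-water t1/2 ratio near 1, with a tight interval from the randomised periods, would support that assumption. Separate summaries cannot show how large a change has been excluded.

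**Working it through.** **1. The plan's own precision figure.** Inputs from protocol 9.2 and Table 5: within-subject CV 35%, N = 12, 90% CI.

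- σ_w = √ln(1 + 0.35²) = 0.340
- SE of the paired log difference = 0.340 × √(2/12) = 0.1388
- t(0.95, 11) = 1.796, so the half-width is 0.249
- Limits = exp(±0.249) = 0.779 and 1.283

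This matches the stated 0.78 and 1.28, and with 11 df it reproduces every row of Table 5. The planned precision is therefore a paired one.

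**2. The same interval for t1/2.** The documents give no CV for t1/2, so a range is shown.

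| Assumed within-subject CV | 12 pairs | 8 pairs |
|---|---|---|
| 15% | 0.90 to 1.12 | 0.87 to 1.15 |
| 35% | 0.78 to 1.28 | 0.73 to 1.38 |
| 50% | 0.71 to 1.41 | 0.64 to 1.56 |

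**3. What a reader could construct from by-regimen summaries alone.** Without the pairing, the two regimens have to be combined as if independent. With within-participant correlation ρ on the log scale (not given in the documents), the total SD is 0.340/√(1 − ρ) and t(0.95, 22) = 1.717. The limits are exp(±1.717 × SD × √(2/12)). The last two columns come from simulation (40,000 trials per setting, 12 complete pairs, log-normal data, CV 35%).

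| ρ | Limits × ratio | 90% CI excludes 1, true ratio 1.5 | 90% CI excludes 1, true ratio 2.5 |
|---|---|---|---|
| paired analysis | 0.78 to 1.28 | 86% | 100% |
| 0.3 | 0.75 to 1.33 | 80% | 100% |
| 0.5 | 0.71 to 1.40 | 69% | 100% |
| 0.8 | 0.59 to 1.70 | 25% | 99% |

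The loss is real for a modest change and practically nil, on this measure, for a large one. With complete data the point estimate is the same either way.

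**4. What the plan already gives on elimination.** SAP Table 3 defines CL as Dose/AUC(0-∞) for IV dosing, and the IV dose is 100 µg in both period 1 and period 2. So CL(IV+ITZ)/CL(IV) = AUC(IV)/AUC(IV+ITZ), the inverse of a ratio that SAP 4.3.6.2 already estimates within participant with a 90% CI. This holds where AUC(0-∞) is derivable; the SAP falls back to a partial AUC otherwise.

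**5. Which interval suits tmax with 12 pairs and no ties.**

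- Order-statistic interval for the median (the kind used in Part B), 3rd to 10th difference: 1 − 2 × P(Bin(12, 0.5) ≤ 2) = 96.1%.
- Next narrower, 4th to 9th difference: 1 − 2 × P(Bin(12, 0.5) ≤ 3) = 85.4%.
- Hodges-Lehmann interval, 18th to 61st of the 78 Walsh averages: 1 − 2 × P(W ≤ 17) = 1 − 2 × 0.0461 = 90.8%.

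The Part B interval cannot come close to 90% with 12 pairs; the signed-rank interval can.

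**The case against.** The strongest reply is that the SAP does what the protocol asks. Protocol 9.4.2 allows descriptive summaries for Part C and names models only for AUC and Cmax. The sample size is justified on those two. The objectives are to characterise a profile, and no hypothesis is tested. Part B differs in having an explicit objective to assess the impact of food. All of this stands: the plan is internally consistent here, and the point is an improvement in estimation.

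A reader might go further and infer that the effect of itraconazole on elimination is left without an interval. The documents do not support that, because the paired IV AUC(0-∞) ratio carries the clearance ratio (step 4). A t1/2 ratio adds information on volume and the terminal phase, but it supplements the clearance result.

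A reader might also infer that the SAP analyses the regimens as independent groups. It does not; it produces the same by-regimen summaries for AUC and Cmax beside their models. Step 3 describes what a reader could reconstruct, not a planned analysis.

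The numbers are also open to challenge. The 35% CV belongs to AUC and Cmax, ρ is assumed, and the 1.5-fold change is illustrative. With a 2.5-fold change, the gap in how often the interval excludes 1 almost disappears. That objection stands, and it limits the claim to modest effects.

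The t1/2 ratios have limits of their own. t1/2 is derived only if data allow, and replacements may enter at a later period, so there may be fewer than 12 pairs. For itraconazole, regimen is confounded with fixed period, as it already is for AUC and Cmax. Sampling also runs to 60 h with itraconazole, against 10 h (IV) and 24 h (oral) without it. No interval reflects those two problems. Finally, full display details are left to the Output and Programming Specification, which is not available; nothing in the protocol or SAP assigns it a tmax or t1/2 contrast.

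**Conclusion.** The gap is real but limited. Two of the listed Part C primary endpoints have no planned within-participant contrast with an interval, although the design provides one and the SAP uses such contrasts elsewhere. It is not a breach of the protocol, and it does not affect AUC, Cmax or the clearance result. The loss is in precision on modest changes in t1/2 and oral tmax, and it is most relevant to GFJ versus water: that comparison is randomised, little change in t1/2 is expected if juice spares the liver, and the width of the interval is what would make the finding informative.

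Under an assumed 35% CV, ρ of 0.5 and 12 complete pairs, the paired 90% CI is 0.78 to 1.28 times the ratio, against 0.71 to 1.40 without pairing. These figures are illustrative, since the documents give neither a CV nor a correlation for t1/2. No comparable size can be given for tmax.

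**What to change.** Keep the by-regimen summaries in SAP 4.3.7.2 and add the following.

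- **t1/2:** where derivable, add log t1/2 to the models in SAP 4.3.5.2 and 4.3.6.2. Report a ratio and 90% CI for PO+GFJ to PO+water, IV+ITZ to IV, and PO+ITZ to PO+water. State the number of pairs for each. Beside the two itraconazole ratios, note that the periods are fixed and are sampled to 60 h, against 10 h (IV) and 24 h (oral).
- **Oral tmax:** report the within-participant Hodges-Lehmann median difference with a signed-rank-based 90% CI for GFJ versus water and for ITZ versus water. Coverage is about 90.8% with 12 untied pairs; ties at scheduled sampling times would make it approximate. Leave IV tmax descriptive, since the 1 h infusion largely fixes it.
- **Estimand table:** update SAP Table 2, Primary 3 and Primary 4, to match.

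The cost is a few lines of SAP text and a handful of extra model runs on data already being collected. Sample size and study conduct do not change. The downsides are that some contrasts may rest on fewer than 12 pairs and that more intervals are reported, none of them a formal test.

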4.3.8. Other Endpoints

4.3.8.1. Endpoints/Variables

Plasma concentration of 4β-hydroxycholesterol and cholesterol, assessed in part B, are considered as a potential *in vivo* marker of CYP3A4 enzyme activity.

4.3.8.2. Summary Measure

The ratio of plasma concentration of 4β-hydroxycholesterol to total cholesterol will be summarised by day and dose (placebo arm will be included). Ratio obtained on day 14 would be divided by the ratio obtained on day 1 to assess the CYP3A4 enzyme activity induction, if 1 indicates no induction.

4.4. Interim Analyses

Details of dose escalation reviews are covered in the dose escalation plan.

4.5. Changes to Protocol Defined Analyses

N/A

5. SAMPLE SIZE DETERMINATION

Twelve, 36 and 12 participants would be randomised to study intervention in parts A, B and C respectively. A further 12 healthy volunteers would be randomised in parts A and B if additional dose levels are required to be studied.

The samples size for part A and B were selected to support the planned assessments of safety and tolerability, the primary objective of parts A and B of the study.

In parts A and B, 9 participants will receive each active oral dose. If 0/9 participants experience a particular adverse event, the upper limit of the exact 95% CI indicates that a true incidence rate of 33.6% could not be ruled out. Whereas if 1/9 participants

experienced an event, the upper limit of the exact 95% CI indicates that a true incidence rate of 48.2% could not be ruled out.

The sample size for part C was selected taking into consideration the precision of estimation of the ratios of AUC and Cmax for the following comparisons of interest.

- GSK3915393 PO + GFJ v GSK3915393 PO + water
- GSK3915393 IV + ITZ v GSK3915393 IV
- GSK3915393 PO + ITZ v GSK3915393 PO + water

Assuming a within subject coefficient of variation of 35%, with 12 subjects the upper and lower limits of the 90% CI for the AUC and Cmax ratios will be 0.78 and 1.28 times the point estimate respectively. Increases in AUC and Cmax are expected to be observed when GSK3915393 is dosed in combination with GFJ or ITZ and it is expected that F_G (ratio of AUC for GSK3915393 PO + water: GSK3915393 PO + GFJ) will be less than 1.

6. SUPPORTING DOCUMENTATION

6.1. Appendix 1 Abbreviations and Trademarks

6.1.1. List of Abbreviations

Abbreviation	Description
AE	Adverse Event
API	Active Pharmaceutical Ingredient
AUC	Area under the concentration time curve
BID	Twice Daily
C τ	Trough Concentration
CI	Confidence Interval
CL	Clearance
C _{max}	Maximum observed concentration
CPMS	Clinical Pharmacology Modelling and Simulation
CSH	Heterogeneous Compound Symmetry
CS	Compound Symmetry
CV	Co-efficient of variation
CYP3A4	Cytochrome P450 3A4
DEC	Dose Escalation Committee
ECG	Electrocardiogram
F	Absolute bioavailability
FA	Product of fraction of drug absorbed
FG	Fraction of drug escaping gut metabolism
FH	Fraction of drug escaping hepatic metabolism
FTIH	First time in humans
GSK	GlaxoSmithKline
GFJ	Grapefruit Juice
HV	Healthy Volunteer
IV	Intravenous
ITZ	Itraconazole
NQ	Non-quantifiable
OPS	Output and Programming Specification
PBO	Placebo
PK	Pharmacokinetics
QTc	Electrocardiogram QT interval corrected from Heart Rate
RD	Repeat Dose
Ro	Observed Accumulation ratio
Rs	Steady state accumulation ratio

Abbreviation	Description
SAP	Statistical Analysis Plan
SAE	Serious Adverse Event
SD	Single Dose
STD	Standard Deviation
$t_{1/2}$	Apparent terminal half-life
T_{max}	Time to maximum observed concentration
VC	Variance Components
V_d	Volume of distribution
β	Beta

6.1.2. Trademarks

Trademarks of the GlaxoSmithKline Group of Companies	Trademarks not owned by the GlaxoSmithKline Group of Companies
None	SAS WinNonlin

